5. Steps in the first 24 hours will be measured using an activity tracker. The Research Coordinator will record mobility data from the tracker to the CRF. Patients in Group 2 will also have steps measured automatically by the RF MAC System. The Research Coordinator will also record mobility reported by the RF MAC system in the patient's CRF.

6. At least once during the first 24 hours of the in-patient period, the Research Coordinator will measure through observation and using a stopwatch, the amount of time required by a nurse to prepare the patient to ambulate (removing tubes, cords, etc.).

7. Prior to discharge, the Research Coordinator will conduct a second 4-meter walk test. Results will be recorded in the patient's CRF.

8. As the patient is preparing for discharge, the Research Coordinator will ask the care team to complete a brief survey regarding their experience with both the standard DVT prophylaxis device and the RF MAC System during their hospital stay.

**At Home:** Once discharged, patients will continue involvement in the study at home. Patients in Group 2 will be sent home with their RF MAC System and a "patient packet" that includes a user manual, charging station, controllers, additional straps, a list of study contacts, a patient self-report journal, instructions for wear time and prescriptive mobility, and instructions for returning their devices and activity tracker at the end of the study. Patients in Group 1 will be sent home with instructions for the standard of care, and instructions on how to return their activity tracker. Patients in both groups will receive orders for standard of care from their healthcare team. This may or may not include IPC DVT prophylaxis for Group 1. Group 2 will receive orders for mobility and use of the RF MAC System. In addition, patients in both Groups 1 and 2 will receive daily at-home mobility goals from their healthcare team.

9. The Research Coordinator will record the prescribed at-home standard of care provided prior to discharge.

10. Patients in both groups will receive orders for at-home physical therapy for a minimum of 14 days, which is standard of care for TJR patients discharged to home.

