11. Group 1 will receive standard of care DVT prophylaxis (which may be compression stockings, standard IPC or no orders) and a daily goal for steps (mobility). Compliance related to DVT prophylaxis will be self-reported by the patient in a journal in terms of total minutes per day. Compliance with mobility goals will be tracked using an activity tracker in addition to being self-reported.

	

12. Group 2 will receive instructions on how many hours per day to use the RF MAC System and a targeted number of steps to achieve per day (from healthcare team). Primary compliance data with DVT prophylaxis will be self-reported in a patient journal. Data related to mobility goals will be collected by the RF MAC System and recorded each day by the patient.

13. A final 4-meter walk test will be administered by the Research Coordinator at the 2-week in-office visit and results will be entered into REDCap.

14. At the end of the study, patients will complete a brief survey regarding their experience with both the standard DVT prophylaxis device and the RF MAC System during their in-home recovery. All participants will receive \$100 as remuneration for their study participation and be asked to sign a compensation receipt form. Participants at Tufts Medical Center will also receive \$21 for parking reimbursement.

15. The home physical therapist will also be asked to complete a brief survey.

--	--

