### **2.3 Secondary**

Measure patient reported outcomes (PRO) of comfort, device acceptance and ease of use and measure nurse perceptions of device acceptance and ease of use and collect feedback from nurses and physical therapists.

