**In-Patient:**

In the pre-operative appointment, the Research Coordinator will enroll participants and they will be randomly assigned to a study group (control or intervention). Patients will be assigned a participant number and that number will be recorded on their Informed Consent and the CRF. Only the Research Coordinators at each site and the PI will have access to the key that connects participant numbers to patient names.

A baseline 4-meter walk test will be performed and the Research Coordinator will enter results in the patients CRF. The protocol for the 4-meter walk test is described in the site protocols found in Appendix A (Tufts Medical Center) and Appendix B (Eskenazi Hospital).

On the day of surgery, the patient will receive standard of care for each site for patients undergoing a THR or TKA. Patients in the control group (Group 1) will receive the site's standard of care IPC for DVT prophylaxis. Group 2 (intervention) will receive the RF MAC System for DVT prophylaxis. In addition, patients in both groups will receive an activity tracker and corresponding waterproof pouch to hold the activity tracker. The display screen of the activity tracker will be covered with tape during the study period. Tape will be removed by Research Coordinators and data will be collected from the device at the end of the study period.

Research Coordinators will be responsible for providing device training to participants prior to discharge. This will be conducted using verbal explanation, demonstration and return demonstration. It is expected to require 10-15 minutes to complete training on the RF MAC System and review all required study materials, the use of the activity tracker and follow-up requirements.

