Prior to discharge, the Research Coordinator will conduct a 4-meter walk test and record the results in REDCap and include a note of any assistive walking device used during the test. The Research Coordinator will also record the information on the display of the RF MAC at time of discharge (Group 2 only) and the number of steps on the activity tracker.

As patients in Group 2 are preparing for discharge, the Research Coordinator will coordinate survey completion for the patient and members of the care team (nurses, physical therapists, etc.).

Patients will receive at home orders for DVT prophylaxis, physical therapy and mobility goals. These orders will be recorded in the patient's CRF by the Research Coordinator. Group 1 will receive standard of care DVT prophylaxis (to be noted in the CRF) and Group 2 will take the RF MAC home to continue DVT prevention using the device.

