Once the walk test is complete, the Research Coordinator will direct the patient to complete a final survey. Next, the patients will return all study equipment (activity tracker and the RF MAC System) to the Research Coordinator. Patients who return all equipment will receive their \$100 remuneration for study participation. Renumeration will be reduced by 50% to \$50.00 for any patients who do not return their equipment. Patients who did not return the devices will receive a postage-paid package for returning both the activity tracker and RF MAC device to Recovery Force. Once the equipment has been received by Recovery Force, the additional \$50 remuneration will be mailed to the participant. In addition, participants at Tufts Medical Center will receive \$21 stipend as reimbursement for parking costs.

Research Coordinators will also send at-home physical therapists of individuals in Group 2 a link to a brief survey about the RF MAC.

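### The discharge patient survey is arranged for Group 2 only, so in-hospital comfort, acceptance and ease-of-use ratings have no concurrent Group 1 data

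*Combined protocol and SAP*

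**What the plan says.** The secondary objective (section 2.3) is to "Measure patient reported outcomes (PRO) of comfort, device acceptance and ease of use and measure nurse perceptions of device acceptance", together with ease of use for nurses and feedback from nurses and physical therapists. It states no between-group hypothesis, and section 7.1 names no analysis for any survey outcome.

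The survey contacts are described in four places:

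- **Discharge, section 2.4 (In-Patient):** "As patients in Group 2 are preparing for discharge, the Research Coordinator will coordinate survey completion for the patient", and likewise for members of the care team.
- **Discharge, synopsis step 8:** "the Research Coordinator will ask the care team to complete a brief survey regarding their experience with both the standard DVT prophylaxis device" and with the RF MAC. No group limit is given, and the patient is not named as a respondent.
- **Two weeks, section 2.4 (At Home):** "Once the walk test is complete, the Research Coordinator will direct the patient to complete a final survey". No group limit is given.
- **End of study, synopsis step 14:** "patients will complete a brief survey regarding their experience with both the standard DVT prophylaxis device and the RF MAC System", with reference to the recovery period at home. No group limit is given.

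On device assignment, section 2.4 (In-Patient) says "Patients in the control group (Group 1) will receive the site's standard of care IPC for DVT prophylaxis", and Group 2 receives the RF MAC. At home, Group 2 keeps the RF MAC, while Group 1 may be given stockings, IPC, or no order for prophylaxis (synopsis step 11 and section 2.4, At Home).

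**The concern.** Comfort, acceptance and ease of use are qualities on which a wearable device could be expected to differ from tethered IPC. The fair time to compare them is the hospital stay, when each arm has a defined device and assignment is by randomisation. If only Group 2 patients are asked at discharge, their ratings stand alone. A favourable score cannot be read as better than standard IPC, because no one on standard IPC was asked the same question at the same time.

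Two further points make this worse. The synopsis and section 2.4 disagree on who answers at discharge, so the two sites could run different surveys. The 2-week patient survey, which does reach Group 1, is described as covering both devices although each patient is assigned one. Discharge ratings that are not collected cannot be recovered afterwards.

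**Working it through.** The plan gives no survey figure to reproduce. The check is mainly a comparison of sections, followed by short arithmetic on what each contact could deliver.

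**1. Who answers, and about what**

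| Contact | Source | Group 1 patients | Group 2 patients | Care team |
|---|---|---|---|---|
| Discharge | Section 2.4, In-Patient | not included | yes | of Group 2 patients |
| Discharge | Synopsis step 8 | not named | not named | yes, both devices, no group limit |
| 2 weeks | Section 2.4, At Home | yes | yes | – |
| End of study | Synopsis step 14 | yes, both devices | yes, both devices | – |

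The two discharge rows cannot both be followed as written. Neither gives Group 1 patients a survey.

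The Group 2 limit does not look like shorthand. In the same part of section 2.4, the pre-discharge walk test carries no group limit, while the reading of the RF MAC display is expressly marked as applying to Group 2 alone.

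**2. Number of patient respondents planned at discharge**

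Table 1 gives 75 per group at each of two sites, so 2 × 75 = 150 per group. By the text, respondents at discharge are 0 of 150 in Group 1 and up to 150 of 150 in Group 2.

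**3. What surveying both groups at discharge would give**

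In SD units of a rating score, the 95% CI half-width for a difference in means is 1.96 × √(1/n₁ + 1/n₂). If all 150 per group respond, this is 1.96 × √(2/150) = 1.96 × 0.1155 = 0.23 SD.

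**4. Why the 2-week survey is a weaker substitute**

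With the plan's 15% dropout, 150 × 0.85 = 127.5, so about 127 per group remain. The share of Group 1 with a compression device to rate at home is not given, so a range is assumed:

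| Assumed share | n₁ | n₂ | √(1/n₁ + 1/n₂) | Half-width (SD) |
|---|---|---|---|---|
| 100% | 127 | 127 | 0.1255 | 0.25 |
| 75% | 95 | 127 | 0.1356 | 0.27 |
| 50% | 64 | 127 | 0.1533 | 0.30 |
| 25% | 32 | 127 | 0.1978 | 0.39 |

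Lost precision is the smaller difficulty. Group 1 patients with a device at home are those whose healthcare team ordered one after randomisation. Comparing them with all of Group 2 no longer compares the randomised groups.

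**The case against.** The strongest reply is that Group 1 is surveyed. The final survey at the 2-week visit and synopsis step 14 carry no group limit, so up to 150 Group 1 patients give end-of-study answers. This stands. A reader might infer from section 2.4 that the secondary outcomes have no control arm at all, or that no difference between groups could be estimated. The documents do not support either reading. The gap is confined to the in-hospital ratings.

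Second, the objective is only to measure these outcomes and collect feedback, all four numerical hypotheses concern other outcomes, and section 7.1 plans no survey test. This also stands, and it keeps the severity low. It does not remove the point: the objective sits inside a randomised comparison of two devices, and ratings from one arm cannot say anything about relative comfort.

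Third, a reader might infer from step 14 that patients will be made to score a device they never wore. The survey forms are not in the documents, and the wording may loosely describe one form shared by the two arms. The text therefore needs clarifying, but it does not show that a faulty instrument is in use.

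Fourth, asking the care team about both devices is reasonable, because staff may handle both across patients. This is accepted, and the step 8 wording on devices is not criticised here.

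**Conclusion.** The point holds for the in-hospital patient ratings. As written, 0 of 150 Group 1 patients and up to 150 Group 2 patients are surveyed at discharge, at the end of the only period when all of Group 1 is assigned standard IPC. The 2-week survey includes Group 1 but does not replace the missing ratings. It is framed around home experience with both devices, and an unstated share of Group 1 may have no IPC to rate.

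Synopsis step 8 and section 2.4 also disagree on the discharge respondents and must be reconciled.

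The conclusion rests on the text alone, because the survey forms are not available. The half-widths assume a roughly continuous rating score, full response at discharge, the plan's 15% dropout at 2 weeks, and the assumed shares above. Only secondary outcomes with no planned test are affected. This is a cheap improvement at the low end of severity.

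**What to change.** - **Section 2.4 (In-Patient) and synopsis step 8:** make the two agree. Patients in both groups complete the same survey before discharge, about the device they were assigned in hospital. State separately which care-team members are surveyed and for which patients. Their survey may keep asking about both devices.
- **Section 2.4 (At Home) and synopsis step 14:** word the 2-week patient survey about the device actually used at home. Device items are skipped, and the reason recorded, if there was none.
- **Sections 2.3 and 7.1:** state that the patient-reported ratings are secondary and descriptive. Report the between-group difference at discharge with a 95% CI, and give the number of respondents per group at each contact.

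The cost is survey wording plus about 150 more brief questionnaires. The coordinator already sees patients in both groups before discharge for the walk test, so no new visit is needed and the extra coordinator time is small.

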**At Home:**

Once discharged, patients will continue involvement in the study at home.

Patients in both groups will receive orders for standard of care from their healthcare team. This may or may not include IPC DVT prophylaxis for Group 1. Group 2 will receive orders for use of the RF MAC System. Patients in Group 2 will be sent home with their RF MAC System and a “patient packet” that includes a user manual, charging hub, controllers, additional straps, a list of study contacts, and instructions for returning their devices at the end of the study. Patients in Group 1 will be sent home with the standard of care (as noted in their CRF)

In addition, patients in both Groups 1 and 2 will receive daily at-home mobility goals from their healthcare team (which were noted in the CRF at discharge).

Patients in both groups will receive orders for at-home physical therapy for a minimum of 14 days, which is standard of care for TJR patients discharged to home. The Research Coordinator will record prescribed physical therapy in the patient’s CRF.

Group 1 will receive standard of care DVT prophylaxis (which may be compression stockings, standard IPC or no orders) and a daily mobility goals. Daily mobility goes are expected to prepare patients to complete 2,000 steps a day by the end of the 2-week study period. Compliance will be measured using the activity tracker provided at study enrollment. Patients will be asked to wear the tracker at all times, except during sleep. At the conclusion of the study, the Research Coordinator will record the total activity per day. In addition, the Research Coordinator at each site will call study participants two times during each week of study participation to ensure participants are wearing the activity trackers.

Group 2 will receive instructions on how many hours per day to use the RF MAC System and a targeted number of steps to achieve per day (from healthcare team). Primary compliance data will be self-reported and collected by the Research Coordinator. Data related to mobility goals will also be collected with the activity tracker. A secondary method of data collection will be the RF MAC System itself. At the end of each day, patients in Group 2 will record the data on the display of the RF MAC System screen, filling in the data for each category in a paper diary provided by the Research Coordinator (provided to Coordinators by Recovery Force). The paper diary will include an image of the screen and users will write the data they see on the screen at the end of each day.

The Research Coordinator will call each participant (in both groups) two times a week during the two-week study. Telephone calls will focus on 1) reminding patients to comply with orders; 2) reminding patients to wear their activity tracker; and 3) reminding patients to comply with DVT prevention orders. The Research Coordinator will answer any questions and confirm the participants are complying with study requirements. The Research Coordinator will also review with the patient the return procedures for the RF MAC, which will involve bringing the device with them to their two-week post-operative office visit.

The patients in both groups will be reminded the day before their 2-week appointment via a telephone call to bring their activity tracker with them to their appointment. The patients in Group 2 will be reminded to also bring back the RF MAC System in its entirety with them to their appointment.

At the 2-week follow up appointment, the Research Coordinator will conduct a final 4-meter walk test. Results will be recorded on the patient's CRF in REDCap.

Once the walk test is complete, the Research Coordinator will direct the patient to complete a final survey. Next, the patients will return all study equipment (activity tracker and the RF MAC System) to the Research Coordinator. Patients who return all equipment will receive their \$100 remuneration for study participation. Renumeration will be reduced by 50% to \$50.00 for any patients who do not return their equipment. Patients who did not return the devices will receive a postage-paid package for returning both the activity tracker and RF MAC device to Recovery Force. Once the equipment has been received by Recovery Force, the additional \$50 remuneration will be mailed to the participant. In addition, participants at Tufts Medical Center will receive \$21 stipend as reimbursement for parking costs.

Research Coordinators will also send at-home physical therapists of individuals in Group 2 a link to a brief survey about the RF MAC.

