### **Study Preparation:**

Training for implementation of the research protocol and all study procedures/documentation forms will be provided by [name], RN. Training for delivering the 4-meter walk test will be provided collaboratively by Drs. [name] and [name].

Product training for the RF MAC device for use in both the hospital and home will be provided to the Research Coordinators at each site by the RF clinical training team.

Study materials, including enrollment forms and surveys will be transferred to REDCap at each site. Each site will receive the following supplies:

- RF MAC Systems to meet patient enrollment goals
- Pedometers
- Waterproof bag for pedometers (worn around the neck)
- Stopwatch timers
- Digital height/weight and BMI scale
- Automated timing gates

- Electrical tape
- Gait belts
- Cones
- Measuring tape
- Measuring wheel
- Postage-paid packaging for returning devices

RF will be responsible for the shipping and installation of the RF MAC hardware. The additional single patient use leg straps will be shipped to each site by RF throughout the study to meet each site's enrollment cadence. The product must be stored in a cool, dry and locked location until they are distributed to participants. Each product package will include a User Manual and the MAC Solution brochure. Patients will also receive a paper journal for recording steps and use of the RF MAC System during the at-home study period.

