time required by acute care nursing staff to get the patient ready to ambulate) for the patients in RF1400 group (Group 2) will significantly outperform those in standard IPC prophylaxis group (Group 1). Similarly for the Aim 2 at-home outcome measures, (minutes of use per day in the first 14 days of at home use and gait speed at 14 days using the 4-meter walk test, Recovery Force hypothesizes that patients in RF1400 group (Group 2) will significantly outperform those in standard of care group (Group 1). All outcomes are continuously measured. To test Aim 2, let  $E_1$  be the indicator variable of group 1 ( $E_1=1$ ) vs. group 2 ( $E_1=0$ ), and  $Y$  stands for the outcome variable,  $Z$  refers to other relevant background and/or clinical variables (age, gender, comorbidities, etc.), the analysis of covariance (ANCOVA) model will be used to assess the difference between groups, i.e., and the team will have  $Y = \beta_0 + \beta_1 E_1 + \beta_2 Z + \varepsilon$ , estimated to give corresponding  $b$  parameters for  $\beta$  by ordinary regression. The significance of coefficient of  $\beta_1$  will be tested to show the group differences. The interaction term of treatment indicator and center indicators will also be tested to examine the homogenous treatment effect across the two study sites. The study was powered assuming 80% of power and 0.05 significance level; the study will require 130 patients per group to detect a medium effect size (EF) of 0.35 difference between groups for a continuously measured outcome. Assuming up to a 15% dropout, each site will enroll 150 patients in each group. The graph below shows the different sample size requirements to detect a certain EF at power of 0.8 or 0.9.

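### Section 7.1 compares at-home minutes of use between groups, but the plan conflicts on how Group 1's minutes are to be recorded

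*Combined protocol and SAP*

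**What the plan says.** **The outcome.** Section 7.1 lists "minutes of use per day in the first 14 days of at home use" beside 14-day gait speed as an at-home outcome on which Group 2 is expected to do better than Group 1. It is to be tested by ANCOVA, and the section adds "All outcomes are continuously measured".

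**Synopsis, Methodology Overview.** Item 11 says of Group 1: "Compliance related to DVT prophylaxis will be self-reported by the patient in a journal in terms of total minutes per day". The At Home paragraph shortly before it includes a self-report journal in the Group 2 packet. For the controls it says only: "Patients in Group 1 will be sent home with instructions for the standard of care, and instructions on how to return their activity tracker".

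**Section 2.4.** Study Preparation says: "Patients will also receive a paper journal for recording steps and use of the RF MAC System during the at-home study period". The At Home text, in the paragraph on Group 1, says: "Compliance will be measured using the activity tracker provided at study enrollment". The daily paper diary is described for the other arm: "patients in Group 2 will record the data on the display of the RF MAC System screen". Both groups are telephoned twice a week, but the calls are described as reminders and confirmation of compliance, not as data collection.

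**The concern.** A between-group comparison needs the outcome recorded in both groups. For the in-hospital period, Section 2.4 says how minutes are obtained in each: interview and observation for Group 1, the device display for Group 2. For the home period it has no counterpart for Group 1. The activity tracker, which the supplies list calls a pedometer, records activity and cannot show how long stockings or an IPC sleeve were worn.

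The Synopsis does name a method for Group 1, but its own take-home list does not supply the journal that the method requires. Site staff could therefore reasonably reach different practices. If controls keep no daily record, their minutes are missing because of the arm to which they were assigned. The dropout weights in Section 7.1 cannot help with an outcome that was never collected in an arm, or in one site's controls.

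**Working it through.** **1. The places side by side, for Group 1 minutes at home**

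- Synopsis item 11: journal, daily total in minutes. Method and unit are both given.
- Synopsis At Home paragraph: no journal listed for Group 1; one is listed for Group 2.
- Section 2.4, Study Preparation: a journal for patients, with no group named. Its stated content is step counts and RF MAC wear, and Group 1 has no RF MAC.
- Section 2.4, At Home, Group 1: activity tracker.
- Section 2.4, At Home, diary: a Group 2 task, with an image of the device screen.
- Section 2.4, At Home, return reminders: Group 1 is reminded to bring the tracker, and no Group 1 journal is mentioned.

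The tracker sentence can be read in two ways. If it covers all compliance, it contradicts Synopsis item 11. If it covers step goals only, which its context favours, Section 2.4 does not say how Group 1's prophylaxis time is recorded. Under both readings a site working from Section 2.4 alone has no instruction to collect it.

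**2. The plan's own sample size**

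Inputs from Section 7.1: standardised difference 0.35, power 80%, significance level 0.05 (sidedness not stated; two-sided assumed).

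- n per group = 2 × (1.960 + 0.842)² / 0.35² = 15.70 / 0.1225 = 128.2, so 129.
- The t-test version gives 129.1, so 130, which is the plan's figure.
- Power at 130 per group = Φ(0.35 / √(2/130) − 1.960) = Φ(0.862) = 80.6%.

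**3. Conditional counts of controls with daily minutes**

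Table 1 in Section 2.4 gives 75 controls at each of two sites. (The last enrolment sentence of Section 7.1 reads differently; Table 1 is used here.) The documents do not say how sites will act, so these are assumptions:

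- Both sites follow Synopsis item 11: up to 150 of 150.
- One follows item 11 and the other Section 2.4 alone: at most 75 of 150, all from one site.
- Both follow Section 2.4 alone: 0 of 150, and the comparison cannot be estimated.

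**4. What partial collection would cost**

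Assume 130 analysable in Group 2, an effect of 0.35, and a share of 130 controls with usable minutes. Power = Φ(0.35 / √(1/n₁ + 1/130) − 1.960).

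| Share of controls | n₁ | Power |
|---|---|---|
| 100% | 130 | 80.6% |
| 75% | 97.5 | 74.3% |
| 50% | 65 | 63.5% |
| 25% | 32.5 | 43.0% |

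The 50% row corresponds to the one-site case and flatters it, because group and site are then partly confounded. If site is adjusted for, the Group 2 patients at the other site add essentially nothing to the group contrast, leaving 65 against 65: Φ(0.35 / √(2/65) − 1.960) = Φ(0.035) = 51.4%. The treatment-by-centre interaction planned in Section 7.1 could not be estimated for this outcome.

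**The case against.** The strongest reply is that the plan does name an instrument. Synopsis item 11 gives the method, unit and frequency for Group 1, and nothing ranks Section 2.4 above the Synopsis. This stands. A reader might infer from Section 2.4 that Group 1 has no way at all of recording minutes; the documents as a whole do not support that.

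The tracker sentence follows directly on a step target and is followed by instructions on wearing the tracker, so it most naturally concerns mobility. Synopsis item 11 makes the same split between journal and tracker. This also stands, and it turns a direct contradiction into silence within Section 2.4. The silence still needs filling.

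The packet lists are weak evidence. The Group 2 list in Section 2.4 omits a journal too, although Group 2 plainly keeps a diary. The Study Preparation sentence names no group, so a reader who concludes that the journal is reserved for RF MAC users is drawing an inference from its content. Granted; but even if Group 1 receives that journal, no field for stockings or standard IPC is described.

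The case report forms and Appendices A and B are not in the text reviewed and might contain a Group 1 minutes field. That cannot be excluded, though Section 2.4 cites the appendices only for the walk test.

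Finally, at-home minutes is named as a compared outcome only in Section 7.1. The Synopsis limits Hypothesis 1 to the hospital stay. Section 2.2 states it without that limit, so the importance of the at-home measure is itself unsettled.

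**Conclusion.** The point holds as an unresolved conflict over how an outcome is measured in the control group. The Synopsis calls for a Group 1 journal, its take-home list does not provide one, and Section 2.4 gives Group 1 only a tracker that cannot measure the quantity.

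The size depends on site practice, which the documents do not establish. The range runs from no loss, if both sites follow Synopsis item 11, to no control data at all, if neither does. The figures of 0 and 75 out of 150 are scenarios, not predictions. The power figures further assume the planned 130 analysable per group and an effect of 0.35.

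Two gaps remain even under the Synopsis reading. Group 2 has a device display as a second source while Group 1 has self-report only. And Group 1 may go home with stockings or with no prophylaxis orders, yet nothing says what minutes of use means for those patients. The matter deserves correction before controls are discharged, because daily minutes that were not recorded cannot be recovered later.

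**What to change.** - Reconcile the Synopsis At Home paragraph and item 11 with the Study Preparation and At Home text of Section 2.4, so that both groups receive a daily journal completed at the same time of day.
- Give the Group 1 version fields for the type of prophylaxis ordered, the minutes used that day, and 'none ordered'. Collect it at the two-week visit and add it to the Group 1 return reminder.
- State in the Group 1 paragraph of Section 2.4 that the tracker measures steps only and the journal measures prophylaxis minutes.
- State in Section 7.1 how Group 1 patients with stockings or no orders enter the minutes-of-use comparison. The 'none ordered' field identifies those without orders but does not settle how they are analysed.

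The cost is a generic version of a paper journal that the study already uses and a few sentences of text. The downside is a small daily burden on Group 1 patients. The change leaves clinical care as it is.
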